A new supplement study is a longitudinal cohort study leveraging the parent study. The objective is to assess the effect of the pandemic on the stability of end-of-life care preferences and on our key outcomes (dyad congruence on goals of care, patient decisional conflict, and surrogate decision-making confidence).

Aim 1. Compare the stability of patients' goals-of-care preferences over time, from pre-outbreak to during-outbreak, by group (SPIRIT vs control) and estimate effect by race (Blacks and Whites).

Aim 2. Assess the stability in the preparedness outcomes (dyad congruence, patient decisional conflict, and surrogate decision-making confidence) comparing pre-outbreak to during-outbreak by group, and estimate race effect.

Aim 3. Examine the associations of the COVID-19 Related Stress questionnaire, sex,

race/ethnicity, and other sociodemographic characteristics (e.g., education level, income) to change in the outcomes and the stability of patients' goals-of-care preferences after the COVID-19 outbreak.

Endpoints:

Primary Endpoints (Aim 1):

Dyad congruence on goals of care, patient decisional conflict, and surrogate decision-making confidence at 2 week post-intervention

Secondary Endpoints (Aim 3):

Surrogate HADS and PTSS scores at 3 months after the patient's death;

Exploratory (Aim 4):

EOL treatment intensity

Supplement Aim:

Dyad congruence on goals of care, patient decisional conflict, and surrogate decision-making confidence at 2-3 day post-intervention

Study Population:

400 patients and 400 surrogates of the patients participate as pairs (400 patient-surrogate dyads); adults (≥ 18 y); both genders; all race and ethnicity; ESRD/chronic dialysis population

For the supplement aims:

30 patients with ESRD + cognitive impairment, including early stages of dementia, who are not eligible for the parent study due to cognitive impairment, and 30 surrogates of the patients as pairs

Supplement cohort study:

~100 dyads who completed the baseline assessment and post-intervention assessment prior to the pandemic lockdown.

Phase:

Phase III effectiveness trial

For the supplement aims, NIH Stage 1 biobehavioral intervention research

**Description of
Sites/Facilities Enrolling
Participants:**

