5 STUDY POPULATION

5.1 INCLUSION CRITERIA

Patient eligibility criteria:

- a) 18 years or older
- b) on either hemodialysis or peritoneal dialysis
- c) able to understand and speak English.

Surrogate eligibility criteria:

- a) 18 years or older (to serve as a surrogate decision-maker, the individual must be an adult)
- b) being chosen by the patient.

Roughly 76 providers at the 29 clinics, including all medical directors, nurse managers, social workers, and those who are selected to conduct SPIRIT sessions will participate in the implementation evaluation.

For Supplement Aims:

Patient eligibility criteria:

- a) Receiving in-center hemodialysis at Emory or UVA dialysis clinics.
- b) Diagnosed with dementia of any etiology (or those for whom their care providers, either MD or APRN, are suspicious of dementia) with having mild to moderate cognitive impairment based on a Montreal Cognitive Assessment (MoCA) score of 13 or higher,^{54,55} or a Saint Louis University Mental Status (SLUMS) score of 21 or higher (high school education) or 20 or higher (less than high school education)⁵⁶
- c) Able to understand and speak English
- d) A UBACC (decision-making capacity screening test) score ≥ 11 . Because dementia is largely under-diagnosed in the clinical setting for patients with ESRD, to identify additional patients with possible dementia, a trained research assistant will administer the MoCA or SLUMS to patients who are suspected (by dialysis clinicians) of having dementia. MoCA or SLUMS will take about 10 minutes to complete.

Surrogate eligibility criteria:

- a) 18 years or older (to serve as a surrogate decision-maker, the individual must be an adult)
- b) being chosen by the patient.

For supplement cohort study:

Dyads who completed the parent study's baseline (T1) and 2-week follow-up (T2) before March 13, 2020.

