At the next monthly check in phone call (as part of the parent study protocol), the research staff member will proceed with the procedures for the parent study and then introduce the participant to the supplement study, including the purpose and procedures and obtain verbal consent. After both members of the dyad have consented, the recruiter will schedule two data collection calls (T3 within 1 week and T4 at 6 months). If additional subjects are needed, we will contact those who already completed the study before the pandemic.

To Maximize Participant Retention, we will

- a) obtain two backup contacts from each member of the dyad in the event that we cannot reach them by telephone and mail
- b) make confirmation phone calls 2 days prior to the baseline and/or the SPIRIT session (intervention group)
- c) make scripted monthly check-in calls
- d) send holiday cards
- e) assign the same data collector whenever possible
- f) provide transportation support (\$20) for the SPIRIT session in person at the center (intervention group)
- g) compensate each member of the dyad with gift cards (\$20 at baseline; \$25 at post-intervention follow-up; and surrogates who complete post-bereavement assessment will receive \$30 at 1 month after the patient's death).

For supplement cohort study, each member of the dyad will receive an additional \$20 at the completion of T3 and \$30 at T4.

Recruitment of Care Providers for Implementation data collection, we will obtain a list of dialysis care providers from each dialysis center, who are willing to be contacted by the study staff for participating in implementation related data collection. This data collection is to obtain inputs from the care providers regarding SPIRIT implementation as part of routine dialysis care. Research study staff at the study site will contact care providers on the list using their preferred contact numbers or emails. Verbal Care Provider Informed Consent will be used in consenting process. Survey/Interviews will be scheduled to be conducted over the phone or in person at the convenience of the Care Provider. There will be no compensation for care provider's participation.

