 - 5) The proportion of decisions made at 6 months (e.g. stopping dialysis, DNR order, and hospice enrollment etc.) follow-up or death of patient will be higher in the intervention dyads than that of control dyads.
- Aim 2:
 - 1) HAD-anxiety scores in SPIRIT surrogates will be lower than those of control surrogates at 1 month after the patient's death.
 - 2) HAD-depression scores in SPIRIT surrogates will be lower than those of control surrogates at 1 months after the patient's death.

Supplement cohort study:

Aim 1. Changes in patient's goals of care preferences over time (T2-T3 and T2-T4) in the intervention group will be smaller than those in the control group.

Aim 2. Changes in the preparedness outcomes over time in the intervention group will be smaller than those in the control group.

Aim 3. The COVID-19 Related Stress and race/ethnicity will be significantly associated with changes in goals of care stability and the preparedness outcomes.

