9.2 SAMPLE SIZE DETERMINATION

We have an adequate sample size to detect clinically meaningful differences between SPIRIT and usual care for our primary outcomes. Statistical power is based on a random effects models: a generalized linear mixed model for binary outcomes (e.g., dyad congruence) and a linear mixed model for continuous outcomes (e.g., patient decisional conflict).

We conducted a simulation study to estimate power with 2-sided significance level alpha=.05, corrected for anticipated dropout and potential intraclass correlations (ICCs) ranging .01-.04, based on ICCs observed in our prior work. To estimate the power more conservatively, we used the effect sizes observed at 2 months²⁰ rather than those at 2 weeks,¹⁸ which are larger (e.g., for the composite outcome, *OR*=1.8 at 2 months, *OR*=4.4 at 2 weeks). The overall power to detect clinically meaningful differences is excellent for the primary outcomes and good for the post-death outcomes.

Power for comparing SPIRIT and usual care with 19 clusters				
Aim 1	Percent or min. difference	OR or variance	ICC ^a	Estimated power
Dyad congruence	48%	OR =2.0	0.02 0.04	0.92 0.84
Patient DCS	d =0.24	0.23	0.01 0.10	0.98 0.81
Surrogate DMC	d =0.22	0.20	0.01 0.10	0.99 0.80
Composite outcome	47%	OR =2.0	0.02	0.93
Aim 3				
Anxiety	d =1.35	7.0	0.01 0.03	0.84 0.80
Depression	d =1.60	10.0	0.01 0.03	0.85 0.79
PTSS-10	d =4.75	90.0	0.01 0.03	0.85 0.78

^a observed ICCs in our prior work; *d*=1/2 *SD*.

DCS, decisional conflict scale; DMC, decision-making confidence.

For Supplement Aims:

Because this is a pilot study, prior estimates of effect sizes were not available; thus a traditional sample size calculation was not performed. Instead we focused on calculating the minimum effect size that can be detected with adequate power (>=80%). Based on preliminary calculations, we found that a sample size of 30 will achieve 80% power to detect an effect size (Cohen's *f*²) of 0.28 (moderate-high), attributable to the treatment group indicator using an F-test at a 5% significance level. We will use the estimates of effect sizes obtained from this study for sample size calculations in future larger studies.

Supplement cohort study:

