Aim 1. Compare the stability of patients’ goals-of-care preferences over time, from pre-outbreak to during-outbreak, by group and estimate effect by race: We will use mixed effects modeling to assess differences in patients’ goals of care over time, from pre- to post-lockdown time points. We will sequentially build a longitudinal model that will include time, treatment group and race as fixed effects; then 2-way interactions of time x group, time x race, treatment x race, and finally a 3-way interaction of time x group x race, if the sample size permits. We will select the most parsimonious model using Akaike information criterion (AIC) and Bayesian information criterion (BIC). We will use contrasts to test whether participants demonstrated significant change in goals-of-care preferences across different combinations of treatment and race.

Aim 2. Assess the stability in the three preparedness outcomes, from pre-outbreak to during-outbreak by group, and estimate race effect: We will perform analyses similar to those described in Aim 1. In addition, for non-normal outcomes (binary, count) a generalized mixed effects model will be used. Appropriate contrasts will be used to assess differences in the outcomes over time by treatment groups, race and groups x race.

Aim 3. Examining the associations of the COVID-19 Related Stress, sex, race/ethnicity, and other sociodemographic characteristics to the level of changes in the preparedness outcomes and patient’s goals-of-care preference stability: We will use analysis of covariance to assess the relationship between COVID-19 related stress and changes in outcomes from T2 to T3 and T3 to T4, after controlling for the corresponding baseline values of the outcomes (i.e., T2 and T3 respectively). Using similar methods, we will evaluate whether there are disparate effects of sex, race/ethnicity and other sociodemographic factors on outcome changes and goals-of-care preference stability from T2 to T3 and T3 to T4, respectively

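### In the COVID-19 cohort, preparedness change is measured from two weeks after SPIRIT, so waning of the SPIRIT effect can be mixed with any pandemic effect

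*Combined protocol and SAP*

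**What the plan says.** **Purpose.** Section 1.1 states: "The objective is to assess the effect of the pandemic on the stability of end-of-life care preferences and on our key outcomes". The key outcomes named there are dyad congruence, patient decisional conflict and surrogate decision-making confidence.

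**Reference visit.** In section 9.1 the Aim 1 hypothesis concerns "goals of care preferences over time (T2-T3 and T2-T4) in the intervention group". The Aim 2 hypothesis names no visit: "Aim 2. Changes in the preparedness outcomes over time in the intervention group will be smaller than those in the control group". Section 9.4.2 says Aim 2 will be analysed along the same lines as Aim 1. Aim 3 will "assess the relationship between COVID-19 related stress and changes in outcomes from T2 to T3 and T3 to T4". Section 8.1 places T2 two weeks after Session II.

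**Timing.** Section 5.1 admits "Dyads who completed the parent study's baseline (T1) and 2-week follow-up (T2) before March 13, 2020". Section 5.5 schedules T3 within a week and T4 at 6 months, and adds: "If additional subjects are needed, we will contact those who already completed the study before the pandemic".

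**Models.** The cohort part of section 9.4.2 lists time, group, race and their interactions for Aims 1 and 2, with adjustment for patient characteristics that differ between groups. Aim 3 is an analysis of covariance on the starting value. No model includes time since T2 or since SPIRIT, and there is no comparison outside the pandemic.

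**Course of the SPIRIT effect.** Section 9.2 says effects at 2 weeks were larger than at 2 months: "for the composite outcome, *OR*=1.8 at 2 months, *OR*=4.4 at 2 weeks". Section 2.2 reports that in the efficacy trial decisional conflict was significantly lower with SPIRIT at 12 months.

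**The concern.** T2 is taken soon after the intervention, when its effect may be near its highest. If the effect then wanes, the SPIRIT arm moves between T2 and T3 whether or not there is an outbreak. Usual-care dyads have no SPIRIT effect to lose. The planned time-by-group contrast would then show more change in SPIRIT, which is the opposite of the Aim 2 hypothesis, and the plan could not tell waning from a pandemic effect. Late growth of the effect would cause the same difficulty with the opposite sign.

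What is at stake is interpretation. The cohort's stated product is a set of effect sizes for pre-outbreak versus during-outbreak change. In the SPIRIT arm, and in any estimate that pools or contrasts the arms, those effect sizes may contain something other than the outbreak.

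**Working it through.** **1. Gap from T2 to T3.** T2 must precede 13 March 2020 (section 5.1). The cohort entered the protocol on 12 August 2020 (section 10.2). Days between: 18 + 30 + 31 + 30 + 31 + 12 = 152, so T3 is at least 5 months after T2 and T4 at least 11. A dyad that had completed the nine monthly calls before the pandemic had its T2 by about June 2019, so its T3 is about 14 months or more after T2. The gap therefore varies widely between dyads.

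**2. The plan's own cohort figure.** Section 9.2 gives 80% power for 72 SPIRIT and 35 usual-care dyads, difference in mean change 0.5, SD 1.0 at both visits, correlation 0.2, 5% level.
- SD of change = √(2 × (1 − 0.2)) = 1.265.
- SE of the group difference = 1.265 × √(1/72 + 1/35) = 0.261.
- Two-sided power = Φ(0.5/0.261 − 1.96) = 0.48.

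The 80% is not reproduced. That is a separate matter. It is relevant here because it shows how little precision there is for extra interaction terms.

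**3. The section 9.2 odds ratios at face value.** ln 4.4 = 1.48 and ln 1.8 = 0.59. The difference is 0.89, about 60% of the 2-week value. Assume a stable control rate of 47% (the power table lists 47% for the composite without naming the arm), so the odds are 0.47/0.53 = 0.887.
- 2 weeks: 0.887 × 4.4 = 3.90, and 3.90/4.90 = 79.6%.
- 2 months: 0.887 × 1.8 = 1.596, and 1.596/2.596 = 61.5%.
- Fall: 18 points. The fall is 22 points at a 30% control rate and 16 points at 53%.

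**4. Chance that such a fall is significant with no pandemic effect.** This uses a normal approximation, 72 and 35 dyads, correlation 0.2, and ignores clustering.
- Variance of SPIRIT change: 0.796 × 0.204 + 0.615 × 0.385 − 2 × 0.2 × √(0.796 × 0.204 × 0.615 × 0.385) = 0.321.
- Variance of usual-care change: 2 × 0.47 × 0.53 × (1 − 0.2) = 0.399.
- Within SPIRIT: SE = √(0.321/72) = 0.0667; Φ(0.181/0.0667 − 1.96) = 0.775 (0.72 to 0.85 for control rates from 53% to 30%).
- Group contrast, in the direction of more change in SPIRIT: SE = √(0.321/72 + 0.399/35) = 0.126; Φ(0.181/0.126 − 1.96) = 0.30 (0.26 to 0.43; 0.38 to 0.62 if the correlation is 0.5).

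**5. Continuous scores.** Decisional conflict and surrogate confidence are scores, and the documents give no 2-week versus later figures for them. Assumed waning of 0.1, 0.25 or 0.5 SD would be significant within SPIRIT with probability 0.10, 0.39 or 0.92 (SE 1.265/√72 = 0.149), and as a group contrast with probability 0.07, 0.16 or 0.48 (SE 0.261).

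**6. What an elapsed-time term can do.** If the loss occurs between 2 weeks and 2 months, it is complete before the shortest gap of 5 months. Gaps of 5 months or more carry no information on it. A months-since-T2 term deals with unequal gaps and later drift only.

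**The case against.** The strongest reply is that waning is not shown. The two odds ratios come from different trials, so the 60% difference is not a within-person decay. The composite, although built from congruence and surrogate confidence, is not one of the cohort's three named outcomes. The efficacy trial's composite estimate is itself imprecise (1.82, 95% CI 1.0 to 3.2, section 2.2), and the documents give no interval for 4.4. For decisional conflict the 12-month result points away from fading. All of this stands, and it limits the point to what can happen.

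T2 is also a defensible reference, because the question is whether positions held after advance care planning survive a disaster. Change from T1 is no cleaner, since in the SPIRIT arm it contains the treatment effect. This stands too.

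Aim 1 concerns the patient's own preferences. SPIRIT is not meant to raise these, and sections 2.1 and 2.2 describe them as generally stable. Aim 1 is therefore largely outside the point.

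Finally, section 9.2 calls the cohort exploratory. That lowers the stakes but does not remove the problem, because the effect sizes it sets out to estimate are the quantities affected.

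A reader might go further and infer that fading will be reported as the pandemic undoing SPIRIT, or that the cohort cannot answer its question. The documents do not support either. Nothing says how a null result would be reported, usual-care change carries no SPIRIT waning, and the COVID-stress analysis in Aim 3 is already planned.

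**Conclusion.** The point holds for cohort Aim 2 and the preparedness part of Aim 3. SPIRIT-arm change from T2, and the time-by-group contrast, can mix waning or late growth of the SPIRIT effect with any pandemic effect, and nothing in the planned models separates them. Waning would bias against the hypothesis of smaller change in SPIRIT, provided the outbreak itself leaves the outcomes unchanged or worsens them.

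The size is unknown for the three named outcomes. As an illustration only, the section 9.2 odds ratios would give a fall of 16 to 22 points in the SPIRIT arm without any pandemic effect. That fall would be significant within the arm about 78% of the time, and as a reversed group contrast about 30% of the time. These figures assume that the cross-trial difference is true waning, a stable control rate (47%, range 30% to 53%), a correlation of 0.2 and no clustering.

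Usual-care change is free of SPIRIT waning, assuming that no usual-care cohort dyad received delayed SPIRIT (section 4.1, Year 4) before T3 or T4. It is worth correcting before analysis because it changes what the cohort can conclude.

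**What to change.** 1. In section 9.4.2, add months from T2 to T3 or T4, taken from recorded visit dates, as a covariate in the Aim 2 and Aim 3 models. Fit its interaction with group only as a sensitivity analysis, given 72 and 35 dyads. State that the term handles unequal gaps and later drift but cannot remove decay completed before 5 months.
2. Report T2–T3 and T2–T4 change separately by arm, with usual-care change presented as the estimate free of SPIRIT waning. Show T1 values beside T2 for context, and say that change from T1 in the SPIRIT arm contains the treatment effect and is not a pandemic estimate.
3. In sections 1.1 and 9.1, describe SPIRIT-arm change and the group contrast as change since T2 during the outbreak period (waning plus pandemic), not as the effect of the pandemic.

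The cost is revised wording, one more model term, a slightly wider interval and a weaker causal claim. No new data are needed.

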9.2 SAMPLE SIZE DETERMINATION

We have an adequate sample size to detect clinically meaningful differences between SPIRIT and usual care for our primary outcomes. Statistical power is based on a random effects models: a generalized linear mixed model for binary outcomes (e.g., dyad congruence) and a linear mixed model for continuous outcomes (e.g., patient decisional conflict).

We conducted a simulation study to estimate power with 2-sided significance level alpha=.05, corrected for anticipated dropout and potential intraclass correlations (ICCs) ranging .01-.04, based on ICCs observed in our prior work. To estimate the power more conservatively, we used the effect sizes observed at 2 months²⁰ rather than those at 2 weeks,¹⁸ which are larger (e.g., for the composite outcome, *OR*=1.8 at 2 months, *OR*=4.4 at 2 weeks). The overall power to detect clinically meaningful differences is excellent for the primary outcomes and good for the post-death outcomes.

Power for comparing SPIRIT and usual care with 19 clusters				
Aim 1	Percent or min. difference	OR or variance	ICC ^a	Estimated power
Dyad congruence	48%	OR =2.0	0.02 0.04	0.92 0.84
Patient DCS	d =0.24	0.23	0.01 0.10	0.98 0.81
Surrogate DMC	d =0.22	0.20	0.01 0.10	0.99 0.80
Composite outcome	47%	OR =2.0	0.02	0.93
Aim 3				
Anxiety	d =1.35	7.0	0.01 0.03	0.84 0.80
Depression	d =1.60	10.0	0.01 0.03	0.85 0.79
PTSS-10	d =4.75	90.0	0.01 0.03	0.85 0.78

^a observed ICCs in our prior work; *d*=1/2 *SD*.

DCS, decisional conflict scale; DMC, decision-making confidence.

For Supplement Aims:

Because this is a pilot study, prior estimates of effect sizes were not available; thus a traditional sample size calculation was not performed. Instead we focused on calculating the minimum effect size that can be detected with adequate power (>=80%). Based on preliminary calculations, we found that a sample size of 30 will achieve 80% power to detect an effect size (Cohen's *f*²) of 0.28 (moderate-high), attributable to the treatment group indicator using an F-test at a 5% significance level. We will use the estimates of effect sizes obtained from this study for sample size calculations in future larger studies.

Supplement cohort study:

Due to the exploratory nature of the study, a traditional sample size calculation was not performed. Instead, our goal was to provide estimates of effect sizes (standardized mean differences between pre- and during- COVID-19 study points) for the outcomes in aims 1-3. Preliminary power calculations based on a two-sample t-test, indicate that a sample size of 72 in the SPIRIT intervention and 35 in the usual care group achieve 80% power to detect a difference in mean changes of 0.5 between the groups. This calculation assumes a repeated measures design with a standard deviation of 1.0 at both time points, a between measurement correlation of 0.2 and a 5% significance level.

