3 OBJECTIVES AND ENDPOINTS

The objective of this multicenter, clinic-level cluster randomized trial is to evaluate the effectiveness of SPIRIT delivered by dialysis care providers as part of routine care in free-standing outpatient dialysis clinics compared to usual care plus delayed SPIRIT implementation. Simultaneously, we will evaluate the implementation of SPIRIT, including sustainability. We will use a Type I effectiveness-implementation hybrid approach^{62,63} that combines testing intervention effectiveness and gathering information about implementation of an efficacious intervention in a real world setting. The short-term goal is to generate sufficient evidence to accelerate the integration of SPIRIT into dialysis practice and policy. We will recruit 400 dyads of patients at high risk of death in the next year and their surrogates from 30 dialysis clinics in 4 states.

OBJECTIVES	ENDPOINTS	JUSTIFICATION FOR ENDPOINTS
Primary		

OBJECTIVES	ENDPOINTS	JUSTIFICATION FOR ENDPOINTS
Examine the effectiveness of SPIRIT compared to usual care on preparedness outcomes for end-of-life decision making (defined as dyad congruence on goals of care, patient decisional conflict, and surrogate decision-making confidence) at 2 weeks post-intervention.	Dyad congruence on goals of care (binary); Patient decisional conflict (scale); Surrogate decision-making confidence (scale) Composite outcome (goals-of-care congruence with confident surrogate; binary)	The primary goal of SPIRIT is to prepare the patient and surrogate for end-of-life decision making. The preparedness outcomes will indicate whether or to what extent SPIRIT accomplished the goal.
Secondary		
Examine the effectiveness of SPIRIT and usual care on surrogates' post-bereavement distress	Anxiety symptom score (HAS-anxiety); Depression symptom score (HAS-depression); Post-traumatic distress symptom score (PTSS)	Surrogate prepared by SPIRIT for EOL decision making should experience less post-bereavement distress.
Evaluate the process outcomes of SPIRIT implementation: during the initial and delayed implementation of SPIRIT	Acceptability, fidelity, intervention costs, and sustainability	Descriptive aim to generate data for translation
Tertiary/Exploratory		

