9 STATISTICAL CONSIDERATIONS

9.1 STATISTICAL HYPOTHESES

- Primary Endpoint(s):
 - 1) The number of SPIRIT dyads who are congruent on goals of care at 2 weeks post-intervention will be significantly higher than that of control dyads.
 - 2) Patient decisional conflict scores at 2 weeks post-intervention will be significantly lower than those of control dyads.
 - 3) Surrogate decision making confidence (DMC) scores at 2 weeks post-intervention will be significantly higher than those of control dyads.

- 4) The number of SPIRIT dyads who are congruent on goals of care and confident surrogate (DMC=3 or higher) at 2 weeks post-intervention will be significantly higher than that of control dyads.
- Secondary Endpoint(s):
 - 1) HAD-anxiety scores in SPIRIT surrogates will be significantly lower than those of control surrogates at 3 months after the patient's death.
 - 2) HAD-depression scores in SPIRIT surrogates will be significantly lower than those of control surrogates at 3 months after the patient's death.
 - 3) PTSS-10 scores in SPIRIT surrogates will be significantly lower than those of control surrogates at 3 months after the patient's death.
- Exploratory: Among patients who have died,
 - 1) The percentage of patients hospitalized during the final month of life in the SPIRIT group will be significantly lower than that in the control group.
 - 2) The percentage of patients admitted to an ICU during the final month of life in the SPIRIT group will be significantly lower than that in the control group.
 - 3) The percentage of patients having intensive procedures during the final month of life in the SPIRIT group will be significantly lower than that in the control group.
 - 4) The length of hospital stay during the final month of life in the SPIRIT group will be significantly shorter than that in the control group.

For Supplement Aims:

- Aim 1:
 - 1) The number of SPIRIT dyads who are congruent on goals of care at 2-3 days post-intervention will be higher than that of control dyads.
 - 2) Patient decisional conflict scores at 2-3 days post-intervention will be lower than those of control dyads.
 - 3) Surrogate decision-making confidence (DMC) scores at 2-3 days post-intervention will be higher than those of control dyads.
 - 4) The number of SPIRIT dyads who are congruent on goals of care and confident surrogate (DMC=3 or higher) at 2-3 days post-intervention will be significantly higher than that of control dyads.

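### Section 9.2 says power rests on the 2-month effects (composite OR 1.8), but the composite row of its power table uses OR 2.0; either the row or the sentence needs correcting

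*Combined protocol and SAP*

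**What the plan says.** Section 9.2 describes a simulation with a two-sided 5% level, allowing for dropout and clustering. On the effect sizes it says: "To estimate the power more conservatively, we used the effect sizes observed at 2 months". It presents these as smaller than the 2-week effects and illustrates this with the composite outcome: "OR*=1.8 at 2 months, *OR*=4.4 at 2 weeks".

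The table that follows is titled "Power for comparing SPIRIT and usual care with 19 clusters". Its composite row shows 47%, an odds ratio of 2.0, an ICC of 0.02 and power 0.93. No row gives the composite power at 1.8, and nothing explains the move to 2.0. The first data column is headed as a percentage or a minimum difference, and the footnote reads "observed ICCs in our prior work; *d*=1/2 *SD". The section concludes: "The overall power to detect clinically meaningful differences is excellent for the primary outcomes".

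The composite has a mixed status. Section 9.1 lists it under the primary endpoints ("congruent on goals of care and confident surrogate (DMC=3 or higher) at 2 weeks post-intervention"), and the objectives table in section 3 includes it in the primary row ("Composite outcome (goals-of-care congruence with confident surrogate; binary"). The primary endpoints in the synopsis (1.1) name only the other three outcomes: "Dyad congruence on goals of care, patient decisional conflict, and surrogate decision-making confidence at 2 week post-intervention".

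**The concern.** The text and the table give different bases for the same power figure. The text claims the conservative choice and prints its value, 1.8. The table uses a larger effect, which is easier to detect. Rounding does not explain the gap: section 2.2 reports the composite odds ratio in the prior efficacy trial as 1.82, which rounds to 1.8 and not to 2.0.

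What is at stake is the accuracy of a stated power, or of its stated justification, for an outcome that two sections list as primary. It also matters during the trial. Section 10.1.6 asks the DSMB to compare accrual and sample characteristics with the power assumptions, so the assumed effect should be unambiguous.

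**Working it through.** **Inputs.** Two-sided alpha 0.05; composite odds ratio 1.8 at 2 months (text) and 2.0 (table); stated power 0.93; 47%; ICC 0.02; 19 clusters (all section 9.2). 400 dyads (section 4.1). Prior-trial composite odds ratio 1.82 (section 2.2). Equal allocation is assumed.

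**The plan's own figure.** The 0.93 comes from a simulation whose dropout rate, ICC scale and covariate adjustment are not printed, so it cannot be reproduced exactly. A plain two-proportion formula with 200 dyads per arm (47% against 63.9%, an odds ratio of 2.0) gives 0.93, but only by ignoring the ICC in that row, so the match confirms nothing. The check below therefore takes 0.93 at an odds ratio of 2.0 as given and changes only the odds ratio.

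**Branch A: the sentence is right and the row should use 1.8.**

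- Noncentrality implied by 0.93: z(0.93) + z(0.975) = 1.476 + 1.960 = 3.436.
- Ratio of effects on the log-odds scale: ln 1.8 / ln 2.0 = 0.588 / 0.693 = 0.848.
- Rescaled noncentrality: 3.436 × 0.848 = 2.914.
- Power: Φ(2.914 − 1.960) = Φ(0.954) = 0.830.
- Miss chance: 1 − 0.83 = 17%, against 1 − 0.93 = 7%.

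Sensitivity of the 0.83:

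| Variation | Power |
|---|---|
| Stated 0.93 is rounded (0.925 to 0.935) | 0.822 to 0.838 |
| Ratio taken on the proportion scale (0.47 to 0.615 against 0.47 to 0.639) | 0.831 |
| Log-odds scale, each odds ratio with its own standard error | 0.835 |
| 47% read as the SPIRIT share and not the control share | 0.833 to 0.837 |
| Odds ratio 1.82 in place of 1.8 | 0.843 |

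**Branch B: the table is right and shows target effects.** The footnote defines the differences as half a standard deviation. Dividing each tabulated difference by the square root of its tabulated variance:

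| Row | Calculation | Result |
|---|---|---|
| Patient DCS | 0.24 / √0.23 | 0.50 |
| Surrogate DMC | 0.22 / √0.20 | 0.49 |
| Anxiety | 1.35 / √7.0 | 0.51 |
| Depression | 1.60 / √10.0 | 0.51 |
| PTSS-10 | 4.75 / √90.0 | 0.50 |

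All five rows are half-SD differences. Observed effects would be unlikely to fall on one standardised value across five outcomes. An odds ratio of 2.0 in both binary outcomes fits the same pattern of chosen targets. On this branch 0.93 belongs to 2.0 and needs no change, but the sentence naming the 2-month effects as the source is inaccurate, and the value used lies above the 2-month 1.8.

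**The case against.** The strongest reply is that the table is plainly built on target effects, so the 2-month sentence is loose wording and no power figure is wrong. The half-SD pattern supports this, and it is at least as likely as the other branch. It does not remove the inconsistency: the sentence still states a source and a degree of conservatism that the composite row does not have.

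A second reply is that the impact is small. This stands. Power of 0.83 is above 0.80, the synopsis does not name the composite as a primary endpoint, and the outcome is measured at 2 weeks, where the cited odds ratio is 4.4. At that value, with 400 dyads, 19 clusters and ICC 0.02, power exceeds 0.999.

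Three stronger readings are tempting, and the documents do not support them.

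- **Power is really 0.70, so the miss chance is 30% and not 7%.** A design effect of 1 + (400/19 − 1) × 0.02 = 1.40 does give about 0.70 at 1.8. The same formula gives 0.83 at 2.0, where the plan's simulation reports 0.93. Setting 30% against 7% mixes two methods. Within either one, the odds ratio alone moves the miss chance from 17% to 30%, or from 7% to 17%.
- **The powers at 2.0 are wrong because a simple formula does not reproduce them.** Multiplying the design-effect variance by a single factor of 0.75 gives 0.920 and 0.843 for congruence and 0.922 for the composite, against the stated 0.92, 0.84 and 0.93. That factor is an assumption, but section 9.4.2 plans covariate adjustment, which could act in this direction. The rows are mutually coherent, and unprinted settings do not show an error.
- **The congruence row has the same mismatch.** Section 9.2 prints no 2-month odds ratio for congruence, so there is nothing to compare.

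The difference between the 19 clusters in the table and the cluster counts by state in section 6.3 is a separate matter and plays no part here.

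**Conclusion.** The inconsistency is real and is visible within section 9.2: the text gives 1.8 as the 2-month composite effect on which power rests, and the table uses 2.0. Either the composite power is overstated by about 10 points (0.83 against 0.93), or the claim that the 2-month effects were used is wrong. The documents do not decide between the two. The 0.83 rests on accepting the plan's own 0.93 and on a roughly unchanged standard error when the odds ratio moves from 2.0 to 1.8; the variations tried give 0.82 to 0.84.

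A reader might infer that the trial is underpowered. That does not follow, because on the plan's own model power stays above 0.80 on both branches. Severity: minor.

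**What to change.** Do one of the following.

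1. If the 2-month effect is the intended basis, rerun the composite row at an odds ratio of 1.8 with the other settings unchanged and restate its power, which should be about 0.83.
2. If target effects are the intended basis, reword the sentence to say that the table uses an odds ratio of 2.0 for the binary outcomes and half-SD differences for the continuous ones. For the composite, say that 2.0 is below the 2-week 4.4 but above the 2-month 1.8, and remove the statement that the 2-month effects were used.

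The cost is one table row and a rerun of the existing simulation, or one sentence. Sample size, hypotheses and analyses stay as they are.
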